7.2.1.6 SFU[6W], SFU[12W], SFU[24W], SFU[36W], SFU[48W], and SFU[60W]

These visits are applicable for all patients unless locally CT-verified PD occurs. In case of PD this visit should be considered the End-of-Study Visit.

If SFU[60W] is scheduled ≥ 76 weeks since Screening this visit should be considered the End-of-Study Visit, *Section 7.2.1.7*.

TIME WINDOWS:

SFU[6W]: 6 weeks (± 7 days) after Sun-Start Visit
SFU[12W]: 12 weeks (± 7 days) after Sun-Start Visit
SFU[24W]: 24 weeks (± 7 days) after Sun-Start Visit
SFU[36W]: 36 weeks (± 7 days) after Sun-Start Visit
SFU[48W]: 48 weeks (± 7 days) after Sun-Start Visit
SFU[60W]: 60 weeks (± 7 days) after Sun-Start Visit

NB: The CT/MRI scans do not have to be done the very same day as the corresponding study visits. However, each CT/MRI scan has to be done within the specified time window for the corresponding visit.

ACTIVITIES AND ASSESSMENTS:

The same activities and assessments will be done at these visits as was done on Sun-Start Visit except for auto- and alloimmunization, *Section 7.2.1.5*. In addition to dispense of sunitinib, the site personnel will collect unused and empty sunitinib packages (distributed at the previous visit) from the patient for drug accountability, *Section 9.1.4*.

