8.5 Removal of Patients from Therapy or Assessment

Patients are free to discontinue their participation in the study at any time. Withdrawal from the study will not affect or prejudice the patient's further care or treatment. Patients may be withdrawn from study treatment and assessments at any time, if deemed necessary by the Investigator.

Patients who discontinue treatment with Intuvax and/or sunitinib for safety reasons (including DLT, see *Section 11.5*) or due to concomitant medication (*Section 9.6*) will not necessarily be considered withdrawn from the study unless there are other reasons for withdrawal. They should return for all following visits and assessments until PD.

Examples of reasons for withdrawal of patients from this study are:

- Progressive disease on sunitinib treatment
- Screening failure
- The decision of a patient to withdraw from the study (i.e. if the patient withdraws informed consent)
- Administration of concomitant medication prohibited by this protocol, *Section 9.6*
- Pregnancy
- Patient is lost to follow-up
- RCC diagnosis is not confirmed by histological findings from the biopsy collected at nephrectomy or, if applicable, from confirmatory pre-study treatment diagnostic biopsy

The reason and date the patient is withdrawn from the study and subsequent planned replacement therapy will be documented in the electronic case report form (eCRF).

All patients that have received IMP must have safety evaluations for 30 days after the last dose of IMP, *Section 11.2*.

If a patient is withdrawn from further assessments, the Investigator should attempt to complete all discharge procedures, i.e. End-of Study Visit. All AEs should be followed up according to *Section 11.2*.

If a patient is withdrawn from the study, all data collected until the time of withdrawal will be used in the analyses.

Survival data (including post-study survival data if applicable) will be collected and analyzed for all patients withdrawn from the study, *Section 11.3*.

Patients randomized to Intuvax who withdraw from the study before administration of the first dose of Intuvax will be considered screening failures. Patients randomized to sunitinib alone who withdraw from the study before any assessments made at the first visit following Screening will be considered screening failures.

Only patients considered screening failures will be replaced.

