9.3 Selection of Doses in the Study

Intuvax

The Intuvax dose to be administered in this study consists of 10×10^6 viable and HLA class II expressing DCs. The outcome of Immunicum AB's first-in-man study of Intuvax in RCC

patients (Protocol No.: IM-101 and EudraCT No.: 2011-002039-25) in which doses of 5×10^6 , 10×10^6 , and 20×10^6 DCs have been administered formed the basis for the dose selection.

The same dose of Intuvax will be injected two (2) times with a 14 ± 3 day interval into the viable part of the renal primary tumor during the period while the patient is awaiting nephrectomy. The patients will receive the vaccine cells from the same batch (i.e. the same donor) at both administrations. A survival of between 24 and 48 hours is expected for the injected DCs after the first vaccination and a considerably reduced survival after the second injection. On the other hand, the second administration triggers the inherent immune response memory initiated by the first administration. A 14 days period between dosing is suggested to avoid administration of a second dose to a patient with an exhausted immune system. This time-window also reflects the time between diagnosis and nephrectomy in routine care.

The suggested dose is also supported by the pre-clinical program on Intuvax that has been performed by Immunicum AB consisting of four (4) studies in rat. In order to mimic the human situation vaccine cells derived from circulating monocytes were used in the proof-of-concept study (VP10-14), the pilot-toxicology study (VP10-17), the toxicology study (VP10-43), and the biodistribution study (AB11-01). The toxicology study VP10-43 did not reveal any major changes in general health status, vital signs and laboratory parameters.

Sunitinib

The sunitinib dose to be administered in this study is in accordance with the SmPC/USPI from start of treatment.

Duration of treatment

Intuvax

Two (2) injections of Intuvax will be administered with 14 ± 3 days interval followed by Nephrectomy in accordance with local routine at least 3 days after the second vaccination and maximum 63 days from Screening.

Sunitinib

Administration to be initiated five (5) to eight (8) weeks after nephrectomy for all patients. Treatment will continue until End-of-Study (78 ± 2 weeks after Screening) unless terminated due to unacceptable side-effects or other reasons. For post study treatment see *Section 9.9*.

Active control, dosage and mode of administration

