9.9 Post Study Treatment

Intuvax is an IMP under development and will consequently not be available for treatment of the patients after study completion.

Immunicum AB will pay the patients' sunitinib treatment during their participation in the study except for US patients who have health insurance that covers these costs as part of standard of care.

After end of study participation, patients will continue treatment in accordance with clinical praxis, i.e. as per local guidelines and Standard of Care.

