6.3 Hypotheses and Statistical Methods

6.3.1 Definitions

Baseline The date of randomization is defined as baseline for OS and 18-month survival rate.

The centrally assessed CT performed at the Sunitinib Start Visit is defined as CT baseline for evaluation of PFS, response rate and TTP after start of sunitinib in intermediate- and high-risk patients

The Screening Visit is defined as baseline for all other assessments than those listed above.

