6.3.5 Primary Efficacy analysis

This is a descriptive proof of concept study and the sample size is not determined based on a statistical power calculation. Even though the trial is descriptive, some exploratory statistical testing will be conducted for primary endpoint, as described below.

Overall Survival

The primary endpoint is median OS, where OS is defined as the time from randomization to the time of death from any cause.

Median OS after randomization in high-risk and intermediate-risk mRCC patients will be calculated and compared overall and by subgroup based on FAS in the following way:

After the last patient has completed the trial, a collection of survival status, for patients still alive when exiting the study will be conducted by [REDACTED] Drug Safety. Additional collections will be conducted up to 5 years after collection of the last patient's 18 months survival data. For patients who die before end of trial, or patients with a known date of death during the additional collection, the survival time will be calculated as the difference in date of death and randomization date plus 1 day. Patients still alive at last contact, either during the trial or at the additional collection, will be censored at last date patient is known alive. Patients that are lost to follow-up during trial, or alive at end of trial where no follow-up information is available will be censored at last date patient is known alive.

Survival functions will be displayed graphically using Kaplan-Meier plots, and life table statistics will be produced including summaries of number of events and censored observations. Estimates of 25%, 50% (median) and 75% percentiles of time of survival with corresponding 95% confidence intervals will be calculated. Additionally, analyses where the survival functions will be compared between Intuvax+sunitinib, vs. sunitinib alone will be conducted using a stratified log-rank test, controlling for strata (high/intermediate-risk patients).

The analyses will be done overall, and separately for high/intermediate risk group of patients.

In addition, the primary efficacy endpoint will be evaluated using the PPS.

The analyses will be conducted using Proc Lifetest, SAS®.

18-month survival rate

18-month survival rate is defined as the proportion of patients alive 18 months after randomization, or probability of surviving beyond 18 months after randomization.

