Exploratory analyses will be conducted where the influence of individual Sunitinib dose density on the outcome of primary and secondary endpoints will be evaluated. This will be done by applying a cox regression overall, including treatment group, strata and average dose density during the time leading up to either event or censoring. Initially a treatment group by dose density interaction will be included, if the interaction term is not significant the interaction will be dropped from the model.

Sunitinib dose density will be derived as the total recorded dose during the time leading to event or censoring divided by the corresponding time period.

These analyses will be conducted for evaluation of primary endpoint and PFS and in addition summary statistics for dose density will be provided split by treatment group and best response rate, ORR and DCR.

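### Sunitinib dose density is averaged over each patient's own time to event or censoring, so its Cox coefficient for OS and PFS can be significant when dose has no effect

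*SAP*

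**What the plan says.** The analysis is in SAP section 6.3, under the heading on the association between sunitinib dose density and the endpoints. It is done by "applying a cox regression overall, including treatment group, strata and average dose density during the time leading up to either event or censoring". Density is the "total recorded dose during the time leading to event or censoring divided by the corresponding time period". A treatment-by-density interaction is fitted first and dropped if not significant. The models are planned for the primary endpoint and for PFS. The visible text gives no landmark, fixed exposure window or time-dependent form.

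Four other provisions determine how this covariate behaves:

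- **OS clock.** SAP 6.3.1: "The date of randomization is defined as baseline for OS and 18-month survival rate". SAP 6.3.5: "the survival time will be calculated as the difference in date of death and randomization date plus 1 day". Sunitinib starts only five to eight weeks after nephrectomy (SAP 4.1).
- **End of recorded dosing.** Protocol 9.3: "Treatment will continue until End-of-Study", which is week 78 ± 2 from Screening. Progression brings it forward (Protocol 7.2.1.6): "In case of PD this visit should be considered the End-of-Study Visit". Later treatment is outside the study (Protocol 9.9): "After end of study participation, patients will continue treatment in accordance with clinical praxis". Survival is followed for years beyond that.
- **Stops and adjustments before PD.** Of patients who stop treatment for safety, Protocol 8.5 says: "They should return for all following visits and assessments until PD". Dose adjustments are allowed (Protocol 9.3), and the standard schedule is four weeks on, two weeks off (Protocol 9.1.5).
- **Patients enrolled before protocol version 4.0.** Intermediate-risk patients who started sunitinib late or never stay in the PFS analysis (SAP 5 and 6.3.6).

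**The concern.** A fixed covariate in a Cox model must be known when the clock starts. This one is known only when the patient's follow-up ends, and its denominator is the outcome time itself. Two patients on the same daily dose get different densities only because one lived longer.

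For OS, the natural reading counts from randomisation. Very early deaths then have almost no dose, because sunitinib has barely begun. Long survivors have a low density because recorded dosing ended long before. For PFS, a patient who stops or reduces sunitinib has a density that keeps falling the longer PD is delayed, which makes a higher dose look harmful. Doses held shortly before an event push the other way. Pre-version-4.0 patients will mostly have little or no recorded dose before PD, so for them density largely records whether sunitinib was started at all.

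At stake is a reported dose effect, or a retained treatment-by-dose interaction, that is an artefact. A null result would be equally uninformative.

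**Working it through.** **Reference value.** The plan has no power or error figure to reproduce for this model. The benchmark is the two-sided 5% level in Protocol 12.1.3. The sample is about 90 patients, 2:1 (SAP 4.2).

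**OS by hand.** With one constant daily dose, density as a fraction of that dose = months on recorded sunitinib ÷ months from randomisation to death. Assume sunitinib starts at month 2.75 and PD comes 9 months later.

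| Death at month | Calculation | Density |
|---|---|---|
| 3 | 0.25/3 | 8% |
| 12 | 9/12 | 75% |
| 24 | 9/24 | 38% |
| 48 | 9/48 | 19% |

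For a patient dosed to week 78 without PD: week 78 from Screening is 17.94 months. With randomisation 7 days after Screening, it is 17.71 months from randomisation. Then (17.71 − 2.75)/24 = 62% and (17.71 − 2.75)/48 = 31%. The dose is the same in all six cases.

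**PFS by algebra.** With a constant rate *d* from sunitinib start to PD at time *T*, density is *dT*/*T* = *d*, so there is no bias. If dosing stops at *s* < *T*, density is *ds*/*T*, and doubling *T* halves it.

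**Null simulation.** There were 1,000 trials per setting (Monte Carlo standard error at 5%: √(0.05 × 0.95/1000) = 0.7 points). The Cox model was stratified by risk group, with treatment and standardised density and a Wald test. Inputs not in the documents:

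- 30 high-risk and 60 intermediate-risk patients, hazard multipliers 1.6 and 0.8
- exponential OS, median 18, 24 or 30 months; median PD 6, 9 or 12 months from sunitinib start; PD–death correlation 0.3, 0.6 or 0.8
- nephrectomy 14–31 days after randomisation
- individual dose intensity 75–100%
- OS censoring at 18–51 months (Q2 2015 to Q3 2019)

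Taken from the Protocol: a further 14–20 days to nephrectomy in the vaccine arm (9.1.1), sunitinib 35–56 days after nephrectomy, and PD dated at scheduled scans ± 7 days. OS used 3 × 3 × 3 = 27 survival settings × 4 dosing patterns = 108. PFS used median OS 24 months.

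| Density as planned | False rejection of dose | HR per SD |
|---|---|---|
| OS, never-starters at zero | 6–61% (above 10% in 83 of 108) | 0.69–1.41 |
| OS, starters only | 5–97% | 0.97–1.85 |
| PFS, even constant dosing | 4–6% | – |
| PFS, 10% stop by month 6, unrelated to outcome | 18–23% | 1.18–1.37 (10% and 20% together) |
| PFS, 20% stop by month 6, unrelated to outcome | 39–52% | as above |
| PFS, step-down to 75% after a mean of 4, 8 or 16 months | 47–98% | 1.27–1.76 |
| PFS, 4/2 cycling only, all events scan-dated PD | 11–24% | 1.09–1.16 |
| PFS, 4/2 cycling only, deaths also counted | 72–78% | – |
| PFS, dose held 2–4 weeks before event in 30–50% of patients with an event | 77–100% | 0.38–0.59 |

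The treatment coefficient rejected in 3–10% of null trials and the interaction in 3–18%. The PFS runs did not include pre-version-4.0 late starters or never-starters, whose number is not given.

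**Second simulation, separately chosen inputs.** There were 1,500 trials per setting, with OS medians of 24 months (intermediate risk) and 10 months (high risk). A covariate fixed at the start rejected in 5.6% (OS) and 6.1% (PFS), so the model itself behaves. The planned density rejected as follows:

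- **OS from randomisation:** 61.5% with constant dosing to week 78, almost all towards protection; 30.3% if dosing also stops at progression, almost all towards harm.
- **OS from sunitinib start:** 100%.
- **PFS at scheduled visits:** 22.4% with 4/2 cycles alone and 99.3% with dose steps added, against 5.4% with truly constant dosing.

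The treatment test was also off in places, up to 18.7%.

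**Remedy tested in the first simulation.** An 84-day window, in patients alive and progression-free at its end, gave OS 4–8% (HR 0.98–1.02) and PFS 4–8% (HR 0.98–1.01). An OS landmark requiring survival only gave 7–83%. With doses held just before events the landmark gave 5–20%; starting the clock 28 days later brought this to 4–7%.

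**The case against.** The strongest counter-argument is that little depends on this. The models are labelled exploratory, SAP 6.4 treats all inference that way, and no visible decision rests on the dose coefficient. The log-rank test, the 18-month z-test and the separate treatment hazard-ratio models do not use this covariate. That stands and limits the consequence. But exploratory status excuses low power and multiplicity, not a coefficient that cannot answer its own question.

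The SAP does not call the covariate fixed, nor say where the OS period starts. However, one average per patient, ending at that patient's own event or censoring, is not a time-dependent covariate. Counting from sunitinib start makes OS worse.

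The magnitudes rest on assumed inputs, span a wide range and go in both directions. That is fair: neither size nor sign can be predicted for this trial. The held-dose scenario has no source in the documents. Also, follow-up is specified in outline (primary analysis at study end, then survival collection for up to five years). The gap in the plan is the handling of never-starters in the OS dose model. Some nearby SAP text is redacted and cannot be checked.

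On the remedy, day 84 is the centre of the 12-week scan window (days 77–91), so landmark membership partly reflects scan timing. A time-dependent cumulative average is an alternative: in the second simulation it gave 3.9–5.8% for OS and 6.5% for PFS. There, however, progression was independent of death. With dosing stopped at PD and PD linked to death, such a covariate would carry the effect of progression. The same independence explains why a week-26 OS landmark requiring survival only looked acceptable there (5.2%).

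**Conclusion.** The concern holds. The covariate as written depends on the outcome, and the resulting dose coefficient is not interpretable for OS or PFS. Under the assumed inputs, false rejection at nominal 5% is 6–61% for OS from randomisation. For PFS it runs from 4–6% with perfectly even dosing to well above 40% with ordinary stops or reductions. The hazard ratio can fall on either side of 1, depending on follow-up length, the link between PD and death, whether never-starters enter at zero, and the pattern of dose changes.

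That the test is invalid follows from the definition. The sizes are illustrative. The damage is mainly to the dose coefficient in this exploratory analysis, less to the interaction and treatment terms of the same model, and not at all to the primary comparisons. It should be corrected, because the fix is cheap and a spurious dose finding is easy to over-read.

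**What to change.** In the SAP text on dose density:

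1. Replace the covariate with recorded sunitinib dose over a fixed number of days from sunitinib start (for example 84), divided by that same number, and count time from the end of the window.
2. In both models include only patients alive and progression-free at the landmark, excluding those with PD dated on or before that day. Being alive is not enough for OS.
3. Keep patients who stopped sunitinib for other reasons, with their lower recorded dose.
4. As a sensitivity analysis, start the clock 28 days after the window in patients still alive and progression-free then.
5. Exclude pre-version-4.0 patients who had not started sunitinib before PD from the dose model, or report them separately.
6. If the present density is kept, use it only as a descriptive summary, with its start and end stated. Do not use the dose model to adjust or explain the primary treatment effect.

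Fix the landmark day in advance; a day outside the 12-week scan window would make membership depend less on scan timing.

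The cost is SAP wording and modest programming, since sunitinib exposure is already collected. Early events leave this analysis: under the assumed inputs 59–75 of 90 patients remained for OS and 62–73 of about 83 starters for PFS (56–70 with the 28-day gap). The question becomes one about early dose. Confounding by the patient's condition remains, so the result stays exploratory.

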6.3.8 Exposure to Treatment

All details collected in relation to the Intuvax vaccination will be listed and tabulated. Nephrectomy data will be listed. Exposure data for sunitinib use will be listed by treatment group and by high/intermediate risk stratum. Duration of sunitinib treatment will be summarised by treatment group and strata. Patient sunitinib compliance will be evaluated summarising the number of dispensed tablets minus the number of returned and lost tablets.

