AEs	X	X ^c	X ^c	X	X	X	X	X ^k	X ^v	X
Diagnosis Confirmation ^f				X						

a Assessment to be completed before nephrectomy and may be done the day before nephrectomy for logistical reasons

Locally analyzed Creatinine for patients included in the study before 28 August 2017 (if performed as part of clinical routine) to be recorded in eCRF

b Height only at Screening. Weight at all visits except for Vacc1 and Vacc2 Visits.

c See specific flow chart, *Table 3*, for detailed instructions on pre- and post-vaccination assessments.

d Physical examination, ECOG performance, and samples for safety lab and urinalyses may be taken the day before vaccination for logistical reasons

Locally analyzed results for Hb, WBC, platelets, PT-INR, and APTT need to be available before vaccination

Locally analyzed results for Hb, WBC, and clinical chemistry might need to be available prior to nephrectomy

- Analysis of coagulation status at Nephrectomy is not necessary provided the patient is not on anticoagulant treatment. For patients on anticoagulants local sampling practice applies.
- e Pregnancy test in blood at Screening, and in either blood or urine at Vacc1 and Vacc2 Visits. The pregnancy test result is needed prior to each vaccination.
 - f Samples for auto- and alloimmunization analyses will be collected prior to vaccination at Vacc1 Visit. Sampling at Sun-Start Visit only applicable for patients randomized to Intuvax.
 - g To be done when the results from all assessments made are available. Telephone contact with patient to inform about treatment and timing of next study visit.
 - h The prescribed dose to be in accordance with the SmPC/USPI including any dose adjustments.
 - i Return of sunitinib not applicable at Sun-Start Visit and Distribution not applicable at End-of-Study Visit. Standard of Care applies after End-of-Study.
 - j Start of sunitinib administration will be dependent on wound healing. The time window for initiation is five (5) to eight (8) weeks after Nephrectomy.
 - k Post-study collection of survival data.
 - l If CT cannot be used for some reason, MRI is acceptable. The same modality has to be used at all visits.

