9.1.5 Administration of Investigational Medicinal Products

Intuvax

After thawing, all suspension in the vial, e.g. one (1) mL is drawn and the injection needle is filled. The vaccination is done into the viable part of the renal tumor using CT or Ultrasound guidance and monitoring for confirmation of administration location. There is no need to flush the needle with saline since the dead space in the needle has been accounted for.

The total volume injected is recorded on a worksheet and in the eCRF at each Vaccination Visit.

The Intuvax administration must be done by a trained and qualified radiologist/urologist/ /surgeon using an antiseptic procedure in a facility equipped for invasive treatment.

Sunitinib

Per oral administration initiated five (5) to eight (8) weeks after nephrectomy for all patients Administered dose should be in accordance with the SmPC/USPI.

In case of unacceptable sunitinib side-effects the standard on/off schedule of 4 weeks on/ 2 weeks off (schedule 4/2) can be changed to 2 weeks on/1 week off (schedule 2/1). Retrospective data from patients treated with schedule 2/1 (50 mg/day) indicates superior PFS compared to those obtained with schedule 4/2. In addition, the reported safety profile and tolerance for schedule 2/1 justify its use in place of schedule 4/2 [29].

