9.7 Treatment Compliance

Intuvax

Administration will be done at the clinic by trained study personnel. Treatment compliance will be accomplished by documenting in record (i.e. the drug accountability, preparation, administration logs, the patients' eCRF and medical records) information on, but not limited to: the batch number of the IMP used, the time-point for preparation/thawing, the time-point for administration, if CT or Ultrasound was used for confirmation of administration location, and signatures of designated site staff preparing and administering the IMP.

Any deviations will be documented on the appropriate eCRF page.

Sunitinib

Patient compliance will be evaluated by unused tablet counts and check of empty packaging. Patients will be asked to return all unused and empty packaging material at the next clinic visit. The number of unused tablets will be counted upon return and recorded in the drug accountability log kept at the site. The sunitinib compliance including any deviations will be documented in the patients' eCRF.

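### SAP 6.3.8 reports a raw count of tablets presumed taken as sunitinib compliance, with no prescribed amount to set it against, so adherence cannot be read from it

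*SAP*

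**What the plan says.** The SAP's rule, in section 6.3.8, is: "Patient sunitinib compliance will be evaluated summarising the number of dispensed tablets minus the number of returned and lost tablets". It gives no prescribed or expected quantity, percentage or threshold, and no rule for dose changes, interruptions or tablet strength. It does not limit the summary to patients who started sunitinib.

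Protocol 9.7 is equally silent on a denominator: "Patient compliance will be evaluated by unused tablet counts and check of empty packaging". It adds: "The sunitinib compliance including any deviations will be documented in the patients' eCRF". Protocol 9.1.4 has patients supplied, visit by visit, with what they need up to the next planned visit.

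The expected number of tablets is not the same for every patient:

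- The flow-chart notes in Protocol 7.2.2 say: "The prescribed dose to be in accordance with the SmPC/USPI including any dose adjustments".
- Protocol 9.1.5 allows a change of schedule for poor tolerance: "4 weeks on/ 2 weeks off (schedule 4/2) can be changed to 2 weeks on/1 week off (schedule 2/1".
- Protocol 9.3 continues sunitinib to End-of-Study "unless terminated due to unacceptable side-effects or other reasons".
- Protocol 7.2.1.6 says of the follow-up visits: "These visits are applicable for all patients unless locally CT-verified PD occurs".
- SAP 4.1 and 6.3.6 explain that, before protocol version 4.0, intermediate-risk patients were to start sunitinib only once progression was confirmed. Some started late and some never did.

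Alongside the count, SAP 6.3.8 summarises duration of sunitinib by arm and stratum. The SAP's dose-density analysis divides total recorded dose by elapsed time. Appendix 1 lists Table 14.3.5.2 (exposure and dose density), a summary of sunitinib doses and a patient-level compliance listing (16.2.5.2). It lists no table of percent compliance.

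**The concern.** Compliance is the amount taken relative to the amount prescribed. A count without that reference rises with every week a patient stays on drug and falls with every reduction or interruption the physician orders, whatever the patient's adherence. SAP 6.3.2 presents descriptive statistics by treatment group and stratum. If one arm stays on sunitinib longer, its tablet count will be higher, and under the label compliance it may look more adherent when it is not. Sunitinib is common to both arms of an open-label trial, so readers will want to know whether patients in each arm took what they were prescribed. The planned summary cannot tell them.

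**Working it through.** The documents state no compliance figure, so there is nothing to reproduce. The check applies the SAP formula to simple cases.

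**Inputs.** Both schedules in Protocol 9.1.5 give 28 dosing days per 42 days: 4/2 is 28 on and 14 off; 2/1 is twice 14 on and 7 off. The documents do not give tablets per dosing day, so one is assumed. Any other constant number scales all counts equally.

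**Formula.** Count = (weeks / 6) × 28 × fraction taken. The alternative is 100 × tablets taken / tablets prescribed over the same weeks.

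| Weeks on drug | Fraction taken | SAP count | Taken / prescribed |
|---|---|---|---|
| 12 | 1.0 | 2 × 28 = 56 | 56/56 = 100% |
| 24 | 1.0 | 4 × 28 = 112 | 112/112 = 100% |
| 48 | 0.5 | 8 × 28 × 0.5 = 112 | 112/224 = 50% |
| 60 | 0.5 | 10 × 28 × 0.5 = 140 | 140/280 = 50% |
| 60 | 1.0 | 10 × 28 = 280 | 280/280 = 100% |

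Rows two and three share a count but differ twofold in adherence. Row four has half the adherence of row one and 140/56 = 2.5 times its count.

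**Arm-level illustration.** This is a simulation of 4,000 trials with 60 and 30 patients (2:1 of about 90), exponential time on drug capped at 62 weeks, and adherence SD 0.10 limited to the range 0 to 1. Everything except the allocation is assumed. The figures are average arm medians of the count.

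- Equal adherence of 85%, median time on drug 48 versus 24 weeks: 181 versus 97.
- Equal median time of 36 weeks, adherence 90% versus 70%: 150 versus 117.
- Adherence 70% with 48 weeks versus 90% with 24 weeks: 147 versus 102, so the less adherent arm scores higher.

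**A built-in arm difference.** Protocol 9.1.1 expects nephrectomy 14 to 20 days later in the vaccine arm, while End-of-Study is timed from Screening. If that delay carries through to sunitinib start, a vaccine-arm patient who stays to End-of-Study takes 14 × 28/42 ≈ 9 to 20 × 28/42 ≈ 13 fewer tablets at identical adherence. That is small against a 60-week total of 280.

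**Does dose density repair it?** Take two patients over 24 weeks (168 days, 112 dosing days) with starting daily dose D. One is ordered, purely for illustration, to take D/2 and takes all of it: 112 × D/2 = 56D. The other is prescribed D and takes it on half the days: 56 × D = 56D. If recorded dose reflects intake, both have density 56D/168 = D/3 per day. Their compliance is 100% and 50%.

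**The case against.** The strongest defence is that this is one line in a descriptive exposure section and will not be read alone. Duration by arm and stratum sits beside it, and dose density, a dose summary and a patient-level listing are planned. Together they would expose differences in duration and in dose. Because supply is tied to the interval up to the next visit (Protocol 9.1.4), the unused count already shows a shortfall against a planned amount; what is missing is the division. All of this stands and limits the consequence. It does not turn the count into compliance, because none of these outputs separates missed doses from ordered reductions.

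A reader might also draw stronger conclusions that the documents do not support:

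- *The count is simply time on drug.* It also moves with adherence, as the 150 versus 117 case shows.
- *Non-adherent patients cannot be identified for the per-protocol set.* SAP section 5 bases exclusions on reviewed protocol deviations, and Protocol 9.7 has compliance deviations entered in the eCRF. No stated rule uses the count.
- *A survival difference cannot be attributed to Intuvax without a compliance measure.* The primary comparison is randomised and made on the full analysis set. Adherence arises after randomisation and helps interpretation; it is not a condition for comparing the assigned strategies.
- *A reduced dose would raise the count by using more, smaller tablets.* The documents give no tablet strengths or tablets per dose.

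**Conclusion.** The point holds as a correction to a descriptive summary. The quantity SAP 6.3.8 calls compliance is the amount presumed taken, and no section of either document divides it by a prescribed amount. It can give the same value at full and at half adherence (112 tablets) and can reverse the order of two patients (56 versus 140). The specific counts assume one tablet per dosing day, and the simulated values rest on assumed treatment times and adherence. The conclusion itself needs only that time on drug and prescribed amount vary between patients, which the protocol provides for. No primary or secondary endpoint, planned between-arm test or stated per-protocol criterion depends on the count, so the efficacy conclusions are not at risk. What is at risk is any statement in the study report about how well patients in each arm adhered to sunitinib.

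**What to change.** In SAP 6.3.8, among patients who started sunitinib, define compliance per patient as 100 × amount taken / amount prescribed. Amount taken is the quantity dispensed less the quantity returned and lost. Amount prescribed covers the same dispensing intervals, with ordered dose changes and interruptions reflected in it. Use mg where tablet strength is recorded. Summarise the percentage by arm and stratum, add a table for it to Appendix 1, and report the raw count separately as amount taken, under exposure.

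First check that prescribed amounts are available. Protocol 13.2 places prescribed treatments and dosage in the medical records, and Protocol 9.7 places tablet counts in a site log, but neither document shows that prescribed mg per interval is in the analysis database. If it is not, there are two fallbacks:

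- Use the planned amount dispensed per interval (Protocol 9.1.4) as the denominator. State that changes ordered within an interval, and visits held off their planned date, will then affect the percentage.
- Relabel the count as exposure and make no compliance statement from it.

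The cost is a wording change, one derived variable and that data check. No treatment rule changes and there is no added burden on patients.
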